2 = moderate: sufficiently discomforting to interfere with normal activities

3 = severe: prevents normal activities

4 = life-threatening

- Its relationship to the study treatment.
- Its duration (start and end dates) or if the event is ongoing, an outcome of not recovered/not resolved must be reported
- Whether it constitutes a SAE (see [Section 10.1.2](#) for definition of SAE) and which seriousness criteria have been met
- Action taken regarding with study treatment

All adverse events must be treated appropriately. Treatment may include one or more of the following:

- No action taken (e.g. further observation only)
- Drug interrupted/withdrawn
- Concomitant medication or non-drug therapy given
- Participant hospitalization/participant's hospitalization prolonged (see [Section 10.1.2](#) for definition of SAE)
- Its outcome (not recovered/not resolved; recovered/resolved; recovered/resolved with sequelae; fatal; or unknown).

Conditions that were already present at the time of informed consent should be recorded in medical history of the participant.

Adverse events (including lab abnormalities that constitute AEs) should be described using a diagnosis whenever possible, rather than individual underlying signs and symptoms.

Adverse event monitoring should be continued following the last dose of study treatment until the participant starts a commercially available MS disease modifying therapy or until their B cells are repleted. Repletion is defined as a concentration > the participant's baseline value prior to starting the IV anti-CD20 mAb or > the lower limit of normal, whichever is observed first.

Once an adverse event is detected, it must be followed until its resolution or until it is judged to be permanent (e.g. continuing at the end of the study), and assessment must be made at each visit (or more frequently, if necessary) of any changes in severity, the suspected relationship to the interventions required to treat it, and the outcome.

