### 1.1 Study design

This is a single-arm, multi-center, prospective study in patients with relapsing multiple sclerosis (RMS) who have been previously treated with anti-CD20 (aCD20) monoclonal antibody (mAb) therapy and have received at least 2 consecutive courses of intravenously administered ocrelizumab or rituximab every 6 months and the last dose is within 4 to 9 months before Baseline/Day 1.

In this study, participants may enroll only if discontinuing aCD20 therapy for reasons other than lack of efficacy or due to certain treatment-emergent adverse events. Reasons for switching may include but are not limited to physician/participant preference, access to commercial drug (e.g., insurance coverage issues) or for other logistical reasons (such as geographical relocation, travel, etc.).

A total of approximately 100 eligible participants will be enrolled as part of this study. Participants will receive open label ofatumumab 20 mg subcutaneous once monthly for 12 months following initial loading regimen of 20 mg subcutaneous doses on Days 1, 7 and 14.

For participants completing the trial, the total duration of the trial will be a minimum of 14 months. This accounts for the:

- 28 day screening period
- 12 month treatment period
- 30 day telephone safety follow-up

Participants are considered as having completed the study after completing the 12 month treatment period and attending the End of Study (EOS) visit. For participants who discontinue study treatment prematurely for any reason before the end of the 12 month treatment period, an EOS visit will be performed within 7 days of study discontinuation.

Additional post-treatment safety follow-up will be applicable for participants who:

[figure not shown]
- Complete the Treatment period and do not continue on any MS disease modifying therapy (DMT)
- Do not continue into the ofatumumab commercial patient services hub within one month of the End of Study (EOS) visit, where the EOS visit is defined as the last patient's last visit (LPLV), which is the last patient's Month 12 visit, or the visit scheduled at the time of study discontinuation.
- Prematurely discontinue study drug and do not continue on an MS DMT.

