## 2 Statistical methods

### 2.1 Data analysis general information

The statistical analysis outlined in this SAP will be performed by Novartis Business Services (NBS) CONEXTS, using SAS® version 9.4 or higher software, and stored in the Novartis Global Programming and Statistical Environment (GPS).

It is planned that the data from all centers that participate in this protocol will be used for analysis.

For continuous variables, summary statistics will include number of participants (n), mean, standard deviation, minimum, 25th percentile, median, 75th percentile, and maximum.

For categorical variables, frequency counts and percentages will be reported.

Unless otherwise specified, summary statistics tables will include change from baseline.

The study will be divided into two phases (the core and post-treatment safety FU phase) for the purpose of preparing the CSR.

- **Core phase:** The core phase will cover the on-treatment period up Month 12 visit date, or EOS date plus the 30 day Safety Telephone FU for participants who discontinue prematurely. The primary objective will be analyzed for the core phase and will be reported in the analysis CSR. All data up to this date will be reported in the analysis CSR.
- **Post-treatment phase:** The post-treatment phase will cover the post-treatment safety follow-up period which extends from the EOS (+ every 3 months) until the date of B cell repletion for study completers until the participant initiates a commercial MS disease modifying therapy or until the end of the safety follow-up for premature withdrawals. This overlaps with the 30 day Safety Telephone FU. All safety data from the EOS to 30 day Safety Telephone FU will be reported as part of the core phase. Post-treatment phase will be reported in the final CSR. Data collected during the post-treatment safety FU will be listed.

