### **2.8.1.2 Other adverse events analyses**

For the legal requirements of ClinicalTrials.gov and EudraCT, two required tables on TEAEs which are not SAEs with an incidence greater than 5% and on treatment emergent SAEs and SAEs suspected to be related to study treatment will be provided by primary SOC and PT.

If for the same participant, several consecutive AEs (irrespective of study treatment causality, seriousness and severity) occurred with the same primary SOC and PT:

- A single occurrence will be counted if there is  $\leq 1$  day gap between the end date of the preceding AE and the start date of the consecutive AE.
- More than one occurrence will be counted if there is  $> 1$  day gap between the end date of the preceding AE and the start date of the consecutive AE.

For occurrence, the presence of at least one SAE/SAE suspected to be related to study treatment/non-SAE has to be checked in a block e.g., among AEs in a  $\leq 1$  day gap block, if at least one SAE is occurring, then one occurrence is calculated for that SAE.

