### Adverse Event End Date Imputation

Imputed date = date part of original date, if complete date

Imputed date = min (completion/discontinuation visit date, DEC 31, date of death), if month is missing

Imputed date = min (completion/discontinuation visit date, last day of the month, date of death), if day is missing

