### 5.1.3 Concomitant medication date imputation

This algorithm is used when *event* is the partial start date of the concomitant medication. The following table explains the notation used in the logic matrix. Please note that missing start dates will not be imputed. Please note that missing start and end dates were not imputed.

	Day	Month	Year
Partial CM Start Date	Not used	MON	YYYY
Treatment Start/end Date (TRTSDT)	Not used	TRTM	TRY

The following the logic behind the imputation of CM end date.

1. If CM end day is missing and CM month and year are non-missing then CM end day was imputed as the minimum of treatment end date and the last day of the month
2. If CM end day and month are missing and CM end year is non-missing then CM end day was imputed as the minimum of treatment end date and the end of the year (31DECYYYY).
3. Missing CM end dates was not imputed.
4. If the imputed CM end date is less than CM start date then impute CM end date as CM start date.
5. Additional condition for Prior MS modifying therapies (CMSCAT = 'OTHER MULTIPLE SCLEROSIS DISEASE MODIFYING THERAPY'): If imputed date after treatment start date TRTSDT, impute as TRTSDT – 1.

The following matrix explains the logic behind the imputation of start date.

	MON MISSING	MON<TRTM	MON=TRTM	MON>TRTM
YYYY MISSING	(1) Uncertain	(1) Uncertain	(1) Uncertain	(1) Uncertain
YYYY < TRTY	(2.a) Before Treatment Start	(2.b) Before Treatment Start	(2.b) Before Treatment Start	(2.b) Before Treatment Start
YYYY = TRTY	(4.a) Uncertain	(4.b) Before Treatment Start	(4.b) Uncertain	(4.c) After Treatment Start
YYYY > TRTY	(3.a) After Treatment Start	(3.b) After Treatment Start	(3.b) After Treatment Start	(3.b) After Treatment Start

1. If the CM start date year value is missing, the imputed CM start date was set to missing.
2. If the CM start date year value is less than the treatment start date year value, the CM started before treatment. Therefore:
  - a. If the CM month is missing, the imputed CM start date was set to the mid-year point (01JulYYYY).
  - b. Else if the CM month is not missing, the imputed CM start date was set to the mid-month point (15MONYYYY).
3. If the CM start date year value is greater than the treatment start date year value, the CM started after treatment. Therefore:
  - a. If the CM month is missing, the imputed CM start date was set to the year start point(01JanYYYY).

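### The AE date-imputation rules in SAP 5.1.2 can put an event's end before its start, and have no repair like the one in the concomitant-medication rules

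*SAP*

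**What the plan says.** **End dates.** SAP 5.1.2 (Adverse Event End Date Imputation) gives "Imputed date = min (completion/discontinuation visit date, last day of the month, date of death), if day is missing" and "Imputed date = min (completion/discontinuation visit date, DEC 31, date of death), if month is missing". The capping visit is not defined there. SAP 1.1 says "Participants are considered as having completed the study after completing the 12 month treatment period and attending the End of Study (EOS) visit"; participants who stop early have their EOS visit within 7 days of study discontinuation.

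**Collection after EOS.** Protocol Table 8-1 marks AE collection at the 30-day call, and Table 8-2 marks it at each safety follow-up visit. Protocol 10.1.1 adds: "Adverse event monitoring should be continued following the last dose of study treatment until the participant starts a commercially available MS disease modifying therapy". B-cell repletion is the alternative stopping point named there. On reporting, SAP 2.1 states "All safety data from the EOS to 30 day Safety Telephone FU will be reported as part of the core phase" and, for the later phase, "Data collected during the post-treatment safety FU will be listed".

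**Start dates.** In SAP 5.1.2, the reference date is first dose when the AE end is on or after first dose. Convention (A) then takes the later of the first of the recorded month and the reference date plus one day. Convention (B) takes the reference date plus one day.

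**Repairs elsewhere.** SAP 5.1.3, end-date rule 4, reads "If the imputed CM end date is less than CM start date then impute CM end date as CM start date". Start-date rule 5 of that section handles the mirror case. SAP 5.1.2 has no counterpart to either.

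**Use of end dates.** SAP 2.8.1.2 separates one occurrence from several by whether there is at most, or more than, a one-"day gap between the end date of the preceding AE and the start date of the consecutive AE".

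**The concern.** The cap assumes that nothing about an AE happens after the completion or discontinuation visit. That is not how this study collects or reports AEs. For an event that begins after EOS, the cap always lies before the start, so the rule returns an impossible date. An event that begins before EOS and ends after it with a partial end date is cut back to EOS, even if its recorded end month is later.

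The start-date point is similar. Adding one day to first dose can carry the imputed start past an end date that is already known. Events on Day 1 are to be expected, since Protocol 4.5 says that systemic injection reactions were generally limited to the first injection.

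The main thing at stake is clean derived data. The one planned summary that an imputed AE end date can change is the occurrence count in the two tables required for ClinicalTrials.gov and EudraCT.

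**Working it through.** The documents state no figure for this rule, so there is none to reproduce. The check applies the stated rules to dates.

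**1. End before start.** Suppose an AE starts after EOS and its end date is partial. The last day of its end month, 31 December of its end year and any date of death are all on or after its start. The minimum is therefore EOS, which is before the start. As a check, take every EOS date in one year, with the start and true end anywhere from EOS+1 to EOS+30. That gives 365 × (30 × 31 / 2) = 365 × 465 = 169,725 cases, and the imputed end precedes the start in all of them. One exception lies outside this grid: if the start is also partial and falls in the EOS month, convention (A) gives the first of that month and no inversion occurs.

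**2. Example.** EOS is 10 June. AE1 starts on 15 June, truly ends on 19 June, and its end is recorded only as June. AE2, with the same PT, starts on 20 June.
- Imputed end: min(10 June, 30 June) = 10 June.
- Duration by SAP 2.1.1.3 (end − start + 1): 10 − 15 + 1 = −4 days.
- Gap: 20 − 10 = 10 days, so two occurrences. The true gap is 20 − 19 = 1 day, so one.

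**3. Day 1 case.** An AE has a partial start in the month of first dose and a known end on Day 1. The reference date is first dose. Convention (A) gives the later of the first of the month and Day 2, which is Day 2. Convention (B), with the month missing, also gives Day 2. The known end is Day 1.

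**4. Analysed time after EOS.** One month is 30.4375 days (SAP 2.1.1.4), and the safety cut-off is last dose + 30.4375 days (SAP 2.1.1.9). Month 12 falls at 1 + 12 × 30.4375 = day 366.25.
- Last dose at Month 12, which Table 8-1 marks: cut-off 366.25 + 30.4375 = day 396.69, so 30.4 days lie after EOS.
- Last dose at Month 11: cut-off 335.8125 + 30.4375 = day 366.25, so 0 days lie after EOS.

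**5. Occurrence counts under alternative rules.** Extend the grid in step 1 with a second same-PT start anywhere from AE1's true end to EOS+30. This gives 365 × 4,960 = 1,810,400 pairs. The grid is uniform and illustrative; it does not estimate incidence.

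| Rule for AE1's end | Mean occurrences | Over-counts | Under-counts |
|---|---|---|---|
| True date | 1.82 | – | – |
| SAP 5.1.2 as written | 2.00 | 18.1% | 0% |
| As written, plus end set to start if earlier | 1.98 | 16.4% | 0% |
| EOS cap removed (month end) | 1.21 | 0% | 61.0% |

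Per EOS date, 900 of the 4,960 pairs are truly one occurrence. The written rule gets only one of these right: 899 / 4,960 = 18.1%. With the guard, 88 are right: (900 − 88) / 4,960 = 16.4%. A cap at EOS+30 gives the same counts as removing the cap, because no second start lies beyond EOS+30.

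An example of the under-count: AE1 runs from 15 to 18 June and AE2 starts on 25 June. The truth is two occurrences, and the written rule gives two. An end imputed to 30 June gives one.

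**The case against.** The strongest reply is that very little depends on these dates, and most of it stands. The main AE tables in SAP 2.8.1 count participants, TEAE status turns on the start date, and no AE-duration summary is planned. Protocol 10.1.1 has each AE followed to resolution, so a continuing event should normally be a single record. A single post-EOS record counts once whatever its end date. Data from the later follow-up are only listed. The capping visit is also undefined: SAP 2.3.1 treats the 30-day call as a separate disposition period, so a definition might resolve part of the problem.

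A reader might go further than the documents allow in five ways:
- **That occurrence counts are inflated in general.** An over-count needs a partial end on the earlier record, a second record of the same SOC and PT in that participant, and a true gap of at most 1 day.
- **That 7–8% of AEs are affected.** Some 30 of about 395 days (7.6%) is a share of time, and it presumes a Month 12 dose.
- **That 3.3% of AEs move out of their recorded month.** The added day does this when first dose is on the last day of a month, but 12/365 is a share of calendar dates.
- **That listings will show ends before starts.** The SAP does not say whether listings print recorded or imputed dates.
- **That moving the cap later has no cost.** Step 5 shows that it can merge separate events.

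None of this removes the defect. Read with SAP 1.1, the rule returns impossible dates for a class of events that the study collects and reports, and the SAP already repairs the same problem for medications.

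**Conclusion.** The concern holds as a minor error in a stated rule. With the capping visit read as EOS, every AE with a known start after EOS and a partial end date gets an end before its start. An AE with a partial start and a known Day 1 end can get a Day 2 start under conventions (A) and (B). Participant counts and TEAE status are unaffected; for the Day 1 case, both Day 1 and Day 2 count as on or after first dose.

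Occurrence counts in the two registry tables can be too high, but only under the three conditions above. The expected size cannot be derived, because the documents give no rate of partial AE dates or of repeated same-PT records. The percentages in the table compare rules on an artificial grid and should not be read as expected error rates.

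**What to change.** Add two lines to SAP 5.1.2:
- If the imputed end date is before the AE start date, set it to the AE start date.
- If the imputed start date is after a known AE end date, set it to that end date.

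Also state which visit the completion/discontinuation visit is.

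The guards remove both inversions. On the illustrative grid, the end-date guard lowers over-counting from 18.1% to 16.4% and creates no under-counting. It does not restore events that span EOS and are cut back to it. Moving the cap to the last AE-collection contact would do that; if the sponsor chooses it, the SAP should state that later imputed ends can merge separate events into one occurrence.

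The cost is a few lines of SAP text and code, with no new data.

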### Imputed Date Flag

If year of the imputed date is not equal to YYYY then date flag = Y

else if month of the imputed date is not equal to MON then date flag = M

else if day of the imputed date is not equal to day of original date then date flag = D

else date flag = null.

### 5.1.3 Concomitant medication date imputation

This algorithm is used when *event* is the partial start date of the concomitant medication. The following table explains the notation used in the logic matrix. Please note that missing start dates will not be imputed. Please note that missing start and end dates were not imputed.

	Day	Month	Year
Partial CM Start Date	Not used	MON	YYYY
Treatment Start/end Date (TRTSDT)	Not used	TRTM	TRY

The following the logic behind the imputation of CM end date.

1. If CM end day is missing and CM month and year are non-missing then CM end day was imputed as the minimum of treatment end date and the last day of the month
2. If CM end day and month are missing and CM end year is non-missing then CM end day was imputed as the minimum of treatment end date and the end of the year (31DECYYYY).
3. Missing CM end dates was not imputed.
4. If the imputed CM end date is less than CM start date then impute CM end date as CM start date.
5. Additional condition for Prior MS modifying therapies (CMSCAT = 'OTHER MULTIPLE SCLEROSIS DISEASE MODIFYING THERAPY'): If imputed date after treatment start date TRTSDT, impute as TRTSDT – 1.

The following matrix explains the logic behind the imputation of start date.

	MON MISSING	MON<TRTM	MON=TRTM	MON>TRTM
YYYY MISSING	(1) Uncertain	(1) Uncertain	(1) Uncertain	(1) Uncertain
YYYY < TRTY	(2.a) Before Treatment Start	(2.b) Before Treatment Start	(2.b) Before Treatment Start	(2.b) Before Treatment Start
YYYY = TRTY	(4.a) Uncertain	(4.b) Before Treatment Start	(4.b) Uncertain	(4.c) After Treatment Start
YYYY > TRTY	(3.a) After Treatment Start	(3.b) After Treatment Start	(3.b) After Treatment Start	(3.b) After Treatment Start

1. If the CM start date year value is missing, the imputed CM start date was set to missing.
2. If the CM start date year value is less than the treatment start date year value, the CM started before treatment. Therefore:
  - a. If the CM month is missing, the imputed CM start date was set to the mid-year point (01JulYYYY).
  - b. Else if the CM month is not missing, the imputed CM start date was set to the mid-month point (15MONYYYY).
3. If the CM start date year value is greater than the treatment start date year value, the CM started after treatment. Therefore:
  - a. If the CM month is missing, the imputed CM start date was set to the year start point(01JanYYYY).
  - b. Else if the CM month is not missing, the imputed CM start date was set to the month start point (01MONYYYY).
4. If the CM start date year value is equal to the treatment start date year value:

- a. And the CM month is missing or the CM month is equal to the treatment start date month, then the imputed CM start date was set to one day prior treatment start date.
- b. Else if the CM month is less than the treatment start date month, the imputed CM start date was set to the mid-month point (15MONYYYY).
- c. Else if the CM month is greater than the treatment start date month, the imputed CM start date was set to the month start point (01MONYYYY).

5. If the imputed CM start date is after CM end date then impute CM start date as CM end date.

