
Table 8-2 Assessment Schedule, Safety Follow-up

Period ¹	Post-Treatment Follow-Up			
Visit Name	Safety Follow-up Visit 1	Safety Follow-up Visit 2		Additional Follow-up Visits ²
Visit (Month)	EOS + 3 Months	EOS + 6 Months		Every 3 months
Visit Window (Day)	±14	±14		±14
Physical Exam ⁵	S	S		S
Vital Signs (including weight)	X	X		X
Routine lab samples including urine	X	X		X
Sample for CD19+ B-cells and CD3+CD20+ T-cells	X	X		X
Total IgG, IgM levels	X	X		X
Urine Pregnancy Test ^{3,5}	S	S		S
Contraception Status ^{4,5}	S	S		S
Concomitant medications ⁶	X	X		X
Adverse Events	X	X		X

X Assessment to be recorded in the clinical database or received electronically from a vendor

¹ Visit structure given for internal programming purpose only

² As needed for the Participants requiring prolonged B-cell plasma level monitoring

³ Pregnancy test is conducted on female Participants only. Urine pregnancy tests will be conducted at all scheduled visits as indicated in [Table 8-2](#). The Participant must contact the Investigator immediately in the case of a positive test for confirmatory testing at the Investigator's discretion.

⁴ Participant's contraception status must be reviewed and documented to ensure method of contraception continues to be appropriate per protocol requirement for highly effective contraception.

⁵ Assessments captured as source data

⁶ Including corticosteroids used to treat MS relapse; any newly started MS treatment as applicable.

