#### 2.4.3 Prior, concomitant and post therapies

Prior and concomitant medications will be summarized in separate tables for the SAF. Medications will be coded using the WHO Drug Dictionary (WHODD). The latest version of which (at the time of the data cut-off) will be used for the reporting activity.

Medications will be classified as prior, or concomitant as follows:

- Prior medications are defined as drugs taken (including MS medication) and stopped prior to first study treatment administration.
- Concomitant medications are defined as drugs taken at least once between first and last study treatment administration (including those which were started prior to first study treatment administration and continued into the treatment period).

Medications will be categorized into one (and only one) of above classes based on recorded or imputed start and end dates.

Medications will be presented in alphabetical order, by medication category, by Anatomical Therapeutic Classification (ATC) codes and grouped by anatomical main group. Tables will show the overall number and percentage of participants receiving at least one treatment of a particular ATC code and at least one treatment in a particular anatomical main group.

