#### **5.1.3.2 Post therapies date imputation**

Same as above.

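### The SAP's date rules for post therapies can place some partially dated therapies begun after the last ofatumumab dose in the treatment period, where they count as concomitant

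*SAP*

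**What the plan says.** SAP 5.1.3.2, headed "Post therapies date imputation", contains only a cross-reference to the rules above it. Those rules, in SAP 5.1.3, work as follows.

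- **Partial starts** are anchored on the first dose. In the year of first dose with the month missing, "then the imputed CM start date was set to one day prior treatment start date" (rule 4.a). In a later year with the month missing, the start is 1 January (3.a). With a known month in a later year, or a later month of the first-dose year, it is the 1st of that month (3.b, 4.c).
- **Partial ends** are capped. With the day missing, "CM end day was imputed as the minimum of treatment end date and the last day of the month" (end rule 1). End rule 2 does the same with 31 December when the month is also missing.
- **Two repair rules** follow. End rule 4: "If the imputed CM end date is less than CM start date then impute CM end date as CM start date". Start rule 5 does the reverse and moves an imputed start that falls after the end back to the end. The SAP does not say which runs first.

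SAP 2.4.3 names post therapies in its title but defines only prior and concomitant. Concomitant means taken at least once between first and last administration. It then states: "Medications will be categorized into one (and only one) of above classes based on recorded or imputed start and end dates".

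Such records are expected. Protocol Table 8-2, footnote 6, on concomitant medications in the Safety Follow-up, reads: "Including corticosteroids used to treat MS relapse; any newly started MS treatment as applicable".

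**The concern.** By definition, a post therapy starts after the last dose. Rules that look only at the first dose cannot use that fact, and a cap at treatment end contradicts it. A replacement MS therapy, or a steroid course given after ofatumumab was stopped, could then appear in the concomitant-medication tables as if given together with ofatumumab.

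The same start date may also feed SAP 2.1.1.7, which measures the post-treatment safety follow-up period from the last dose to the start of a commercial MS therapy. A start imputed before the last dose would give that period a zero or negative length.

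**Working it through.** The plan states no figure on this point, so the check is to run the rules.

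**Inputs.** Start rules 1 to 5 and end rules 1 to 4 come from SAP 5.1.3, and the definition of concomitant from SAP 2.4.3. The SAP does not define treatment end date. It is taken as the last administration because SAP 2.1.1.9 equates the safety cut-off (counted from treatment end) with the efficacy cut-off of 2.1.1.8 (counted from last administration). A date equal to the last-dose date is read as concomitant.

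**Worked cases.** Cases a to f: first dose 15 Nov 2021, last dose 16 Nov 2022. Case g: first dose 10 Feb 2022, last dose 10 Jun 2022. In every case the therapy truly began after the last dose.

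| Case | Recorded | Imputed | Class |
|---|---|---|---|
| a | start 20 Dec 2022, end Jan 2023 | end capped at 16 Nov 2022, reset by end rule 4 to 20 Dec 2022 | after last dose, but lasts one day |
| b | start Dec 2022, ongoing | 1 Dec 2022 | after last dose |
| c | start Nov 2022 (true 28 Nov), ongoing | 1 Nov 2022 | concomitant |
| d | start 2022, ongoing | 1 Jan 2022 | concomitant |
| e | start 2023, ongoing | 1 Jan 2023 | after last dose |
| f | start Dec 2022, end Jan 2023 | end rule 4 first: 1 Dec 2022; start rule 5 first: 16 Nov 2022 | after last dose; concomitant |
| g | start 2022, ongoing | 9 Feb 2022, the day before first dose | concomitant |

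Cases c, d and g come from the missing floor on the start. The cap on the end changes the class only in case f, and only under one rule order. In case a it distorts the duration alone.

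**Share affected, given a partial date.** Assume true starts are uniform over 1 to W days after the last dose, and last-dose dates are spread evenly over the calendar.

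- *Day missing, ongoing.* Misdated when the start falls in the month of the last dose. The days left in that month average (30.4375 − 1)/2 ≈ 14.7. The share is 14.7/W: 14.7/30 = 49%, 14.7/90 = 16%, 14.7/180 = 8%.
- *Month missing, ongoing.* Misdated when the start falls in the calendar year of the last dose. The share is about 1 − [(W + 1)/2]/365: 1 − 15.5/365 = 96%, 1 − 45.5/365 = 88%, 1 − 90.5/365 = 75%.
- *Both days missing.* As for day missing if end rule 4 runs first. If start rule 5 runs first, 100%, because the end is always cut back to the last dose and the start follows it.
- *Complete start, partial end.* 0%.

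A simulation of the full rules (40,000 records per setting; last dose 120, 335 or 365 days after first dose) gave 49%, 16% and 8% for day missing, and 96%, 87% and 75% for month missing. The timing of the last dose made almost no difference.

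**Follow-up period (SAP 2.1.1.7).** In case c the true value is (28 Nov − 16 Nov) + 1 = 13 days. With the imputed start it is (1 Nov − 16 Nov) + 1 = −14 days. The SAP does not say whether imputed dates enter this formula.

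**The case against.** The case for leaving the text alone has several parts.

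- *Most records are safe.* This stands. Complete dates are untouched, a complete start is protected by end rule 4, and a day-missing start in a month after the last-dose month stays after the last dose unless both dates are partial and start rule 5 runs first.
- *Partial dates should be rare.* These therapies begin during prospective follow-up, and Protocol 11.2 provides for queries on missing values. Year-only starts, which give the highest shares, are the least likely. This is plausible, but the documents give no frequency either way.
- *The tables are descriptive, and part of the data are only listed.* SAP 2.1 says data collected in the post-treatment safety follow-up will be listed. Exposure in tables is therefore mainly to records around the EOS visit and the 30-day call. This stands and limits the effect.
- *Counting an uncertain drug as concomitant is a cautious convention.* That is reasonable when nothing else is known. It is not when the record shows that the therapy was newly started after the last dose.

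A reader might infer more: that therapies begun after ofatumumab are generally counted as concomitant, that the end cap alone pulls them in, or that participants would be taken for users of prohibited medication and lose data from the primary analysis. The rules do not support the first two, as the worked cases show. On the third, SAP Table 5-5 acts on the recorded protocol deviation and its date, and nothing there derives the deviation from imputed medication dates.

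**Conclusion.** The point holds in limited form. SAP 5.1.3.2 states a rule that is wrong for its purpose. It can date a therapy begun after the last dose into treatment in three situations: day missing in the month of the last dose; month missing with a start year that overlaps treatment; and both dates partial with start rule 5 run first. With a complete start and a partial end, only the duration is wrong.

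The shares above are conditional on a partial date and rest on evenly spread start times and on treatment end meaning last dose. The absolute number of records cannot be derived from the documents. The effect is on the concomitant-medication tables and on any period that uses the start of a commercial MS therapy. The visible primary and secondary endpoints do not use these dates. It is worth correcting because the change is small, but it does not threaten the trial's main results.

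**What to change.** 1. Replace the cross-reference in SAP 5.1.3.2. For a therapy recorded as newly started after the last dose, set start = max(01MONYYYY or 01JANYYYY, last dose date + 1). Set end = min(last day of month or 31DEC, last contact date, date of death), not before the start and not capped at treatment end. SAP 5.1.2 already limits adverse-event end dates by the completion or discontinuation visit and death, and end rule 5 of 5.1.3 already gives prior MS therapies their own safeguard, so a direction-specific rule fits the document.
2. Add a post class to SAP 2.4.3 for drugs first started after the last administration. Without it, a correctly dated post therapy still has no class.
3. State that end rule 4 runs before start rule 5.
4. As a minor correction, make the start-date matrix agree with the text. For a start in the month and year of first dose, the matrix points to 4.b and the text to 4.a. This is separate from the main point.

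With items 1 and 2, no therapy recorded as started after the last dose can be dated into treatment, by construction. The cost is SAP wording and a few lines of programming before database lock, with no new data.
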